10.3 Tertiary Endpoints

10.3.1 Changes in BoneHealth

This will be expressed as a difference between the mean T scores on bone densitometry at baseline and at 2 years of follow-up (Section 8.0). A 95% confidence interval for the difference will be constructed using the standard approach for paired measurements [67]. We will also compute the frequency and the percentage of subjects with osteopenia (T score = -1.0 to -2.5) and osteoporosis (T score < - 2.5) at baseline and at 2 years of follow-up.

10.3.2 Changes in Comprehensive Geriatric Assessment

Analysis of this aim will be descriptive and will describe mean, median, standard deviations of scores at baseline and at follow up time points. CGA deficits over 6 months will be captured. Each domain will be evaluated individually and scores will be compared between baseline and 6 months. Overall CGA deficits will be examined and the proportion of patients who decline in more than 1 domain will be determined for these time points.

10.3.3 Quality of Life

This will be measured by the FACT-P tool. (70)For each of the 27 core items and 12 site-specific items, mean score for the study cohort will be computed at baseline and at specified follow-up visits (Section 8.0). These means will be plotted against follow-up time and visually assessed for evidence of an upward or a downward trend. For each item, an upward or a downward trend in mean scores over time will indicate improvement or deterioration in a given dimension of quality of life (i.e., the dimension measured by that item). Changes in mean scores from baseline will be calculated at 3 months and at 6 months after therapy initiation and will be reported with 95% confidence intervals.

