2.3 Tertiary Objectives (Exploratory)

- To determine if the study drug combination affects bone health
- To determine if the study drug combination affects comprehensive geriatric assessment domains
- To determine if the study drug combination affects quality of life

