9.3.3 Quality of life assessments- Functional Assessment of Cancer Therapy - P

The FACT-P is a multidimensional, self-reported quality of life instrument specifically designed for use with prostate cancer patients. It consists of 27 core

items which assess patient function in four domains: Physical, Social/Family, Emotional, and Functional well-being, which is further supplemented by 12 site specific items to assess for prostate related symptoms. Each item is rated on a 0 to 4 Likert-type scale, and then combined to produce subscale scores for each domain, as well as a global quality of life score with higher scores representing better quality of life.

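### FACT-P is analysed only item by item (39 means); the subscale and global scores described in Section 9.3.3 get no analysis, so the quality-of-life objective has no pre-specified summary result

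*Combined protocol and SAP*

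**What the plan says.** Section 2.3 lists the exploratory objective: "To determine if the study drug combination affects quality of life".

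Section 9.3.3 describes the instrument. The 27 core items fall under four headings: "Physical, Social/Family, Emotional, and Functional well-being, which is further supplemented by 12 site specific items to assess for prostate related symptoms". Each item has a rating from 0 to 4. On scoring, the section says the items are "combined to produce subscale scores for each domain, as well as a global quality of life score with higher scores representing better quality of life".

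Section 10.3.3 is the only analysis text for this endpoint. It starts from single items: "For each of the 27 core items and 12 site-specific items, mean score for the study cohort will be computed". This is done for the baseline visit and for each follow-up visit in Section 8.0. The next step is graphical: "These means will be plotted against follow-up time and visually assessed for evidence of an upward or a downward trend". A rise or fall in an item's mean is read as improvement or deterioration in the dimension of quality of life which that item measures. The last step supplies the intervals: "Changes in mean scores from baseline will be calculated at 3 months and at 6 months after therapy initiation and will be reported with 95%". The section contains no subscale or global score, lead score, scoring or missing-item rule, or statement on multiplicity.

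The Section 8.0 footnotes tie FACT-P to the geriatric assessment: baseline, end of cycle 1, every 24 weeks until week 61, and at progression.

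**The concern.** The endpoint definition and the analysis use different units. Section 9.3.3 builds a small number of scores; Section 10.3.3 analyses the raw items and stops there. An analyst following the plan would produce 39 trend plots and a long table of item-level intervals, with nothing to say how they combine into an answer to the objective. Any summary would have to be chosen after the item results were visible, among 39 items, several subscales and a total.

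The contrast with Section 10.3.2 is instructive. There the geriatric assessment is summarised by domain, by overall deficits, and by the proportion of patients declining in more than one domain. FACT-P gets no such summary, although preserving quality of life is part of the rationale in Section 1 for avoiding ADT.

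Direction is a smaller gap. Section 9.3.3 attaches its higher-is-better statement to the combined scores. Section 10.3.3 applies upward-is-better to every item without stating how items are scored.

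**Working it through.** The plan gives no sample size, power or alpha for FACT-P, so there is no planned figure to reproduce.

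**Inputs from the documents.** 27 core and 12 prostate items; intervals at 2 times; 95% level; 40 patients to be recruited, with 36 used in the Section 10.1 calculation.

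**Count.** 27 + 12 = 39 items. 39 x 2 = 78 intervals.

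**Intervals excluding zero if nothing changes.** Expected number: 78 x 0.05 = 3.9, or 39 x 0.05 = 1.95 per time point. This does not depend on correlation between items.

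**Chance of at least one.** If independent, 1 - 0.95^78 = 98.2%. Items of one questionnaire in the same men will be correlated, and the documents give no correlation. A simulation of 78 equally correlated normal statistics gave:

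| Assumed correlation | Chance of at least one |
|---|---|
| 0 | 98.2% |
| 0.2 | 94.9% |
| 0.4 | 83.1% |
| 0.6 | 59.8% |
| 0.8 | 33.7% |

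**Same measures for the Section 9.3.3 scores.** Four domains, the prostate item set and the global score make 6 (counting the prostate set as a score is a reading of 9.3.3).

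| Analysis | Intervals | Expected by chance | At least one, if independent |
|---|---|---|---|
| Single items | 78 | 3.9 | 98.2% |
| Six scores | 12 | 12 x 0.05 = 0.6 | 1 - 0.95^12 = 46% |
| Global score alone | 2 | 2 x 0.05 = 0.1 | 1 - 0.95^2 = 9.75% |

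Six scores without a lead reduce the multiplicity but do not settle it.

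**Precision (illustrative).** The documents give no standard deviation for FACT-P. Assume an item-change SD of 1.0 and 36 patients with data. The half-width is t x SD / sqrt(n) = 2.03 x 1.0 / 6 = 0.34 on the 0 to 4 scale (0.27 to 0.41 for SD 0.8 to 1.2). For the mean of all 39 items, the SD is multiplied by sqrt((1 + 38r)/39). With SD 1.0, the half-width is 0.12 at r = 0.1 and 0.22 at r = 0.4.

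**Schedule.** Assume cycle 1 ends near week 13, which fits the 12-week dispensing interval. Counting back from week 61 in steps of 24 also gives weeks 37 and 13. With time since start = (week - 1) x 7 / 30.44, weeks 13, 37 and 61 are 2.8, 8.3 and 13.8 months. With the 4-week window, the week-37 visit can come no earlier than week 33, which is 7.4 months. On this reading no scheduled FACT-P visit falls at 6 months, and 39 of the 78 intervals have no scheduled data. If the 24-week steps were instead counted from baseline, week 25 (5.5 months) would serve, but week 61 would then be off the grid. The week columns of the calendar table could not be read in the available text, so this rests on the footnotes.

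**The case against.** The strongest reply is that this is an exploratory endpoint in a single-arm phase 2 study, analysed descriptively. Section 10.3.3 has no test, alpha, threshold or decision rule, and trends are judged by eye. No claim depends on an interval excluding zero, and 3.9 of 78 is just the nominal 5%. That stands. A reader might infer that the plan has a 98% false-positive rate for quality of life; the documents do not support this, because no error rate is being controlled or spent and 98% needs an implausible independence.

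A reader might also infer that the intervals are uninterpretable, or that the trial cannot answer its quality-of-life question. Neither follows. Each interval is a valid description of one item, and the subscale and global scores can be computed from the responses already planned. Nor is the analysis confined to two times: item means are computed and plotted at all FACT-P visits, and only the intervals are tied to 3 and 6 months.

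It could also be argued that the closing reference to mean scores in Section 10.3.3 covers the combined scores. The only means defined in that section are item means, so item-level intervals are the natural reading. If combined scores were meant, the text should say so.

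None of this supplies the missing summary. That the scores can be derived later is a reason to fix the choice now.

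**Conclusion.** The point holds as a gap in pre-specification. Section 10.3.3 does not carry forward the scores that Section 9.3.3 defines, and no summary result is planned for the quality-of-life objective. The consequence is up to 78 unadjusted descriptive intervals, about 3.9 of which would exclude zero if nothing changed, with no rule for reading them together. The 3.9 follows from the documents' counts and the 95% level alone. The chance of at least one (98% to about 34%) depends on assumed correlations between 0 and 0.8, and the precision figures on an assumed SD. The primary endpoint, safety analyses and data collection are unaffected.

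The possible absence of a 6-month FACT-P visit is a secondary point and conditional on cycle 1 ending near week 13.

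**What to change.** In Section 10.3.3:

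- Name change from baseline in the FACT-P global (total) score as the lead quality-of-life summary, with 95% intervals at the chosen times.
- Report the Section 9.3.3 subscale scores as supportive, also with 95% intervals.
- State that scoring, item direction and missing items follow the instrument's rules.
- Keep single-item means and plots as a descriptive listing, and drop the reading of each item as its own quality-of-life dimension.

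At the same time, reconcile the 6-month interval with the FACT-P schedule in the Section 8.0 footnotes, either by tying the intervals to named study weeks or by clarifying which visit serves as 6 months. The same footnote governs the geriatric assessment, so the 6-month comparison in Section 10.3.2 should be checked too.

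The scoring change costs only wording, uses the same data and needs fewer intervals. The schedule point is also only wording if the intervals are moved to existing visits.

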¤ After disease progression, follow-up will occur every 6 months (+/- 2 months) for first year after disease progression and as clinically indicated thereafter. Each subsequent antineoplastic therapy and survival status are the only required data point following progression.

¤ Comprehensive geriatric assessment (CGA) will be performed at baseline, end of cycle 1 and every 24 weeks during the study protocol until week 61 and at the time of progression. FACT-P will be performed along with CGA

¤ DEXA scan must be obtained within 2 years prior to registration for all patients. Follow-up DEXA scans should be obtained after 2 years of protocol treatment for patients not receiving denosumab or bisphosphonates. DEXA scan is not indicated for those who are on treatment with bisphosphonates or denosumab.

¤ For patients without radiographic evidence of metastatic disease at enrollment of study protocol, disease assessment with radiographic studies are not necessary unless there is evidence of PSA progression (see Section 6.0) or clinically indicated. For patients with radiographic evidence of metastatic disease at enrollment of study protocol, disease assessment with radiographic studies should be performed as indicated in the above study calendar and may be performed more frequently if clinically indicated by the same methods used at baseline. Chest Imaging may include either chest X-ray or CT chest at the discretion of the treating physician. After week 97, for patients with stable PSA, scans to be performed at the time of progression or as clinically indicated

¤ Treatment will be given daily and will continue until disease progression or other reason for discontinuation of protocol treatment (see Section 7.4) Study drug will be dispensed every 12 +/- 4 weeks and a 120 day supply of medication will be provided at each visit.

¶ This procedure is not mandatory but should be discussed with all patients enrolled in the protocol and can also be considered during the treatment course to prevent further worsening of breast tenderness when considered appropriate..

¤ Followed until death, study closure, or withdrawal of consent.

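### Quality-of-life trends are read by eye from means of a shrinking group of men, so the plotted line can move when no man has changed

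*Combined protocol and SAP*

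**What the plan says.** Section 10.3.3 takes each of the 27 core and 12 site-specific FACT-P items, computes a cohort mean at baseline and at each follow-up visit, and continues: "These means will be plotted against follow-up time and visually assessed for evidence of an upward or a downward trend". It then fixes the interpretation: "an upward or a downward trend in mean scores over time will indicate improvement or deterioration in a given dimension of quality of life". The only quality-of-life estimates with an interval are early ones: "Changes in mean scores from baseline will be calculated at 3 months and at 6 months after therapy initiation", with 95% confidence intervals. The section does not say that these changes are within-patient. It gives no rule for missing forms, no number assessed per visit, and no interval on the plotted line.

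The timing comes from the footnotes to the study calendar (section 8.0). The geriatric assessment (CGA) is done at "baseline, end of cycle 1 and every 24 weeks during the study protocol until week 61 and at the time of progression", and "FACT-P will be performed along with CGA". After progression, "Each subsequent antineoplastic therapy and survival status are the only required data point following progression". For men who stop treatment for another reason, the footnotes list physical examinations and PSA, and no FACT-P.

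**The concern.** A mean at a late visit and a mean at baseline are comparable as a measure of change only if they describe the same men. Here the later group is smaller by design, because progression, toxicity, withdrawal or death ends the scheduled forms. Those reasons may be related to health. The plotted line therefore mixes two things: change within men, and change in which men are being averaged. The reading rule in section 10.3.3 attributes all of it to the first.

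The trial has a single treatment regimen and no control group, so no comparator shares the attrition. Effect on quality of life is a stated exploratory objective (section 2.3), and sparing men the burden of ADT is central to the rationale (section 1.0). A claim that quality of life held up or improved would be drawn from this plot.

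**Working it through.** The documents give no expected completion rate, SD or precision for FACT-P, so there is no planned figure to reproduce. The size is worked out from the PSA-PFS assumptions in section 10.1.

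**Inputs**
- PSA-PFS under the null: median 1.44 years, 1-year rate 50%. Under the alternative: median 3.04 years, 1-year rate 72% (section 10.1).
- These pairs disagree under a constant hazard. A 3.04-year median gives a 1-year rate of 0.5^(1/3.04) = 80%, and a 1.44-year median gives 0.5^(1/1.44) = 62%. Both readings are carried through.
- Visits: 12-week cycles are inferred, since cycle 9 falls at week 97 = 1 + 8 × 12. End of cycle 1 is then week 13, and 24-week steps give weeks 37 and 61. The calendar table is broken in the text available, so this rests on the footnote.
- Week 61 is 60 weeks after the start: t = 60/52.18 = 1.15 years. Week 13 is t = 12/52.18 = 0.23 years.
- Baseline gap g between men who stay and men who leave: 0.25 to 0.5 SD. This is an assumption.

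**Formula.** Let p be the share still assessed, S the baseline mean of stayers and L that of leavers, with g = S − L. The whole cohort starts at pS + (1 − p)L. If nobody changes, the later mean is S. The apparent rise is S − [pS + (1 − p)L] = (1 − p) × g.

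**Week 61, progression only**

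| Assumption | Still assessed, p | Lost, 1 − p | Rise, g = 0.25 | Rise, g = 0.5 |
|---|---|---|---|---|
| Alternative, median 3.04 | 0.5^(1.15/3.04) = 0.769 | 23.1% | 0.06 SD | 0.12 SD |
| Alternative, 72% at 1 year | 0.72^1.15 = 0.685 | 31.5% | 0.08 SD | 0.16 SD |
| Null, median 1.44 | 0.5^(1.15/1.44) = 0.575 | 42.5% | 0.11 SD | 0.21 SD |
| Null, 50% at 1 year | 0.50^1.15 = 0.451 | 54.9% | 0.14 SD | 0.27 SD |

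**Week 13, the 3-month estimate.** The same steps give p = 0.949 and 0.927 under the alternative, a rise of 0.01 to 0.04 SD. Under the null, p = 0.895 and 0.853, a rise of 0.03 to 0.07 SD.

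**Other losses.** Section 10.1 allows up to 10% withdrawal or loss in the first year. Carrying that forward as a yearly rate (an assumption) multiplies p at week 61 by 0.9^1.15 = 0.886. At the 72% rate p becomes 0.607, with a rise of 0.10 to 0.20 SD. At the 50% rate p becomes 0.399, with a rise of 0.15 to 0.30 SD. The progression-only figures are therefore the lower ones.

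**The form at progression.** Each man who progresses should give one more FACT-P at that time. It falls off the visit grid, and nothing says whether it joins the nearest visit's mean, is shown separately, or is left out. The plotted line depends on that choice.

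**Contrast within the plan.** For bone density, section 10.3.1 specifies a paired analysis. Section 10.3.3 has no such wording.

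**The case against.** The strongest reply is that the direction and size of the shift rest wholly on an assumed gap. A reader might infer that the men who leave are the sicker ones and that the plot will therefore show false improvement. The documents do not support that step. The main route off study is a PSA rise, with or without radiographic change (sections 6.0 and 7.4), and section 1.0 describes older patients as often free of cancer symptoms. If leavers and stayers score alike at baseline, the shift is zero; if leavers score higher, the line falls. This stands: the defect is that the rule cannot tell the two sources of movement apart, not that it is known to flatter the treatment.

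A reader might also infer that quality-of-life data simply stop at progression. They do not, because one form is taken then; its use is what is undefined. Nor can the distortion be extended to two years: no scheduled FACT-P falls after week 61, so no such point would be plotted.

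It might be said that section 10.3.2 treats CGA identically. It does not. It has no plot and no rule for reading a trend, and the proportion of men declining in more than one domain is a within-patient measure. Only the means, medians and standard deviations listed over time share the weakness.

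Finally, the shifts are small against sampling error. With 0.685 × 40 = 27.4 men, the 95% half-width of a single mean is 1.96/√27.4 = 0.37 SD. That is true, but the plan puts no interval on the plotted line, so a reader judging it by eye would not see this.

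**Conclusion.** The point holds as a minor one. Following section 10.3.3 exactly, a trend can appear, or a real one be masked, through change in who is assessed. Under the alternative the artefact at week 61 is about 0.06 to 0.16 SD, and under the null about 0.11 to 0.27 SD. These figures assume exponential PSA-PFS, loss through progression only, no use of the at-progression form in the visit means, and a baseline gap of 0.25 to 0.5 SD that the documents neither state nor exclude. The 3-month change is little exposed. The endpoint is exploratory, and neither the primary analysis nor the sample size is affected.

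**What to change.** In section 10.3.3, replace the visual reading of cross-sectional means with mean within-patient change from baseline, in men with both values, with a 95% CI and the number of men at each scheduled visit. Report the form taken at progression separately, or state the rule by which it enters. Remove the sentence that equates a trend in cohort means with improvement or deterioration. Confirm which scheduled visit supplies the 6-month change, since the footnote as read here gives weeks 13, 37 and 61.

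Preferably add a mixed model for repeated measures on the FACT-P scores, giving model-based change with a 95% CI at each visit.

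In section 10.3.2, apply paired change and the number of men per visit only to the means, medians and standard deviations listed over time. Leave the proportion declining in more than one domain as it is.

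The cost is slightly more analysis and no new data. Paired change removes the shift in case mix but not bias from leavers declining faster, and the mixed model relies on data being missing at random. Both limits should be stated with the results.

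### The quality-of-life analysis turns trends read by eye in 39 FACT-P item means into improvement or deterioration, with no criterion for a trend and no link to the planned confidence intervals

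*Combined protocol and SAP*

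**What the plan says.** Section 2.3 sets the exploratory objective: "To determine if the study drug combination affects quality of life". Section 10.3.3 gives the analysis in four steps.

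- Scores: "For each of the 27 core items and 12 site-specific items, mean score for the study cohort will be computed at baseline". The same is done at later visits.
- Display: "These means will be plotted against follow-up time and visually assessed for evidence of an upward or a downward trend".
- Interpretation: "For each item, an upward or a downward trend in mean scores over time will indicate improvement or deterioration". This applies to the dimension which that item measures.
- Estimation by confidence interval: "Changes in mean scores from baseline will be calculated at 3 months and at 6 months after therapy initiation and will be reported with 95%". The closing figure is the confidence level.

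Section 9.3.3 says that items are scored 0 to 4 and combined into subscale scores and a global score, with higher meaning better. Section 10.3.3 does not use those combined scores.

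The Section 8.0 footnotes give the timing. The geriatric assessment "will be performed at baseline, end of cycle 1 and every 24 weeks during the study protocol until week 61 and at the time of". The last of these occasions is disease progression. The questionnaire shares this schedule: "FACT-P will be performed along with CGA".

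**The concern.** The interpretation sentence is the only one that turns the data into an answer to the objective, and sampling error plays no part in it. The mean of an item that is truly flat still moves from visit to visit in a cohort of 40. With 39 items plotted, some will look like steady rises or falls by chance. The intervals in the same paragraph do carry sampling error, but nothing says they govern the conclusion. An item could be written up as deteriorated while its own interval covers zero.

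The neighbouring sections do not have this feature. Bone health (10.3.1) rests on a paired 95% interval, and the geriatric assessment (10.3.2) is declared descriptive.

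The trial has a single arm, so no control group would expose a chance trend. Preserved quality of life is also part of the rationale in Sections 1.0 and 1.3. What is at stake is how the quality-of-life result is read, not the primary result.

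**Working it through.** The plan states no error rate for quality of life, so there is no figure to reproduce. The check asks how often different meanings of trend would be met with no true change and no missing data.

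**Inputs from the documents.** 27 + 12 = 39 items, scored 0-4; 40 men planned (36 before allowance for loss). Visits are read as weeks 0, 13, 37 and 61, because 13 + 24 = 37 and 37 + 24 = 61. The calendar's week labels are broken, so these weeks are an inference.

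**Assumptions.** Item spread and correlations are not given. The simulation cut a latent normal score to 0-4. Inter-item correlation was 0, 0.3 or 0.6, the stable within-man share 0.5 or 0.7, with 1,000 replicates per setting.

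**1. Strictly monotone mean over four visits.** For four exchangeable means without ties:

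- Per item: 2/4! = 2/24 = 0.083.
- Expected items: 39 × 0.083 = 3.25.
- At least one, if items were independent: 1 − (1 − 2/24)^39 = 0.966.
- At least one, continuous scores with inter-item correlation 0.3, n = 40: 0.92-0.93 (simulated).
- Scores 0-4, n = 36-40 (simulated): 0.053-0.060 per item, about 2.1-2.3 items (39 × 0.053 to 39 × 0.060), and 0.71-0.91 for at least one. Ties between visit means pull the rate below 0.083.

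**2. Fitted line explaining more than half the variance of the four means.** Per item 1 − √0.5 = 0.293, so 39 × 0.293 = 11.4 items. At least one item qualifies in 99% or more of simulated trials.

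**3. Sign of the slope.** At n = 36-40 each item has a non-zero slope with probability 0.998-0.999, so essentially all 39 are called.

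**4. Does sample size help?** With n = 400 and 0-4 scores, 3.06 items are monotone (3.06/39 = 7.8%) and 11.3 pass the R-squared criterion. Ten times as many patients does not lower the rate, because precision is not an input.

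**5. Would the planned intervals, applied item by item, cure it?** Two time points give 78 intervals.

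- Expected false calls: 78 × 0.05 = 3.9.
- At least one, if independent: 1 − 0.95^78 = 0.982. Simulated at n = 36-40: 0.78-0.98.
- That is no better than reading 1.

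**6. One global score at two time points.** The Bonferroni bound is 2 × 0.05 = 0.10. Simulated with a summed score: about 0.08-0.11.

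**7. Timing.** Six months is about week 26. With the calendar's ±4-week window, the week-13 visit spans weeks 9-17 and the week-37 visit spans weeks 33-41. On the inferred schedule no FACT-P visit falls at 6 months.

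**The case against.** The strongest reply is that the text does not say every drift counts. Means are "visually assessed for evidence of an upward or a downward trend", which allows a reader to see none. The next sentence can be taken as explaining direction: up is better, down is worse, in line with the scoring in Section 9.3.3. On that view a reader might go too far by inferring that the rule has no null result, or that false declarations are almost certain. The documents do not support either inference. A null result is undefined, not excluded. Near-certainty follows only from the sign-of-slope or R-squared readings, which the plan does not state.

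A second reply is that the intervals at 3 and 6 months show sampling error for two named changes. It would therefore be too strong to say that the plan cannot address its objective. That is right.

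A third is that the endpoint is tertiary, with no alpha, decision rule or stopping rule attached, and that descriptive plots with intervals are acceptable for such a purpose. That limits the importance of the point.

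What stands is narrower. The plan states a rule for interpretation, the rule has no criterion, and the intervals that could supply one are not connected to it.

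**Conclusion.** The point holds as a weakness in an exploratory analysis. Section 10.3.3 allows chance drift in any of 39 item means to be reported as improvement or deterioration. It has no trend criterion, no stated outcome of no clear change, no allowance for the number of items, and no link to its own intervals.

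The size depends on what the reader counts as a trend. Under strict monotonicity over four visits it is about 5-8% per item and roughly 0.7-0.93 for at least one item. These figures rest on assumed correlations, the inferred visit weeks and complete data. They illustrate the problem and are not the error rate of the rule as written, which cannot be computed.

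The problem is not only multiplicity: a single flat score plotted over four visits would still be strictly monotone about 8% of the time, whatever the sample size. The primary endpoint is untouched.

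**What to change.** Amend Section 10.3.3 as follows.

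- Keep the item means and plots, as description only.
- Base the conclusion on the global FACT-P score already described in Section 9.3.3. State improvement or deterioration only where the planned 95% confidence interval for paired change from baseline excludes zero. Otherwise report no clear change, with the interval.
- Tie the two intervals to visits at which FACT-P is actually given under Section 8.0.
- If any item-level change is to be declared, adjust for the number of items. Bonferroni over 78 intervals would use 0.05/78 = 0.00064 each.

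The cost is a few sentences and the scoring of a total that the instrument already provides, with no new data. There will be fewer item-level statements. With two time points, about a 10% chance of at least one false call on the global score remains unless one time point is named as primary.
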